15.4.2 Statistical Hypothesis, Model, and Method of Analysis

Up to 28 patients will be enrolled and treated with the goal of accruing 20 patients that will receive at least 6 vaccines (3 pre-surgery and 3 post-surgery). Less than 20% of patients are expected to drop out between enrollment and the 6th vaccination.

Initial Study Monitoring For Adverse Events: Initially 6 subjects will be accrued to the study after which accrual will be suspended until the last patient enrolled undergoes surgical resection to review the toxicity experienced by these subjects during the first 3 vaccinations. During this period of time, some of the 6 patients may have initiated post-surgery treatment with TMZ and IDH1 vaccine. If 2 or less of these subjects experience an unacceptable toxicity, accrual will continue. Otherwise, modifications of the protocol will be considered before accruing additional subjects. If a patient who has not experienced an unacceptable toxicity does not complete 3 vaccinations, that patient will be replaced for initial study monitoring.

Overall Adverse Event Monitoring: Rigorous monitoring of long- and short-term toxicities in a manner similar to that found in many phase I dose-escalation studies would require accrual suspension between stages of patient accrual while relevant data matures. After the initial 6 patients are accrued and safely receive vaccine treatment, accrual will not be suspended to formally assess the toxicity profile unless the following guidelines are satisfied. Rather, the study will be monitored continuously for the occurrence of unacceptable adverse events.

Once accrual is resumed after the initial monitoring of the first 6 subjects, aggregate summaries of adverse experiences will be generated and reviewed by the clinical team every 6-12 months. The following are considered adequate documentation of review:

- PI review of the aggregate summary of adverse events that is generated every 6 months for the DSMBplus meeting.
- PI signature of the collective AE listing after review with the clinical research team. As described in Section 13.1.1, the PI will periodically review the collective adverse event listing with the clinical research team with the intention of identifying any trends or patterns in toxicity on a monthly basis.

Any patient who discontinues vaccination prior to the receipt of 6 vaccines will not be evaluable for the primary endpoint, unless the patient experienced an unacceptable toxicity. Per Section 12.6.3, these patients will be replaced. Patients who are determined at the time of surgery to have transformed from

Grade II to a higher grade will receive TMZ and radiation therapy per standard of care and monthly vaccines and will be included in the final analysis of the primary objective.

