9.6 Definition of Evaluable Subjects, On Study, and End of Study

For the initial monitoring of adverse events (see Section 15.4.2), evaluable patients will include the first 6 accrued patients who received 3 vaccinations or experienced an unacceptable toxicity due to one of the first 3 vaccinations.

For the final analysis of the primary objective (See section 15.4.2), evaluable patients will include all patients who received at least 6 vaccinations or experienced an unacceptable adverse event that was related to vaccine (or vaccine + TMZ).

Once the patient signs ICF, that subject will be considered "on study." Rationale for taking patient off protocol treatment will be documented. End of study is defined as 2 months following last vaccine for purposes of toxicity monitoring.

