12.6 Early Withdrawal of Subject(s)

12.6.1 Criteria for Early Withdrawal

Subjects may voluntarily withdraw from the study at any time. The PI may also withdraw a subject from the study at any time based on his/her discretion. Reasons for PI-initiated withdrawal may include, but are not limited to the following:

• Progressive disease as documented by MRI or physical examination at any time after the initiation of post-op immunotherapy or post-RT immunotherapy (for those who've transitioned to a higher grade at time of surgery)

- Development of unacceptable toxicity, as defined in section 9.1.1
- Pregnancy
- Need for corticosteroids > 4mg/day at time of 1st vaccine
- Upon request of the subject
- If, in the investigator's medical judgment, further participation would be injurious to the subject's health or wellbeing
- Development of intolerable symptoms
- Protocol deviation
- Administrative reasons, such as a major violation of the clinical trial protocol
- Non-compliance of the subject
- Clinical decline or inability to be weaned off steroids following surgery
- Failure to undergo surgery following the 3rd vaccine
- Failure to tolerate TMZ therapy.

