15.1 Analysis Sets

Subject to the availability of data, all patients who receive any protocol treatment will be included in analyses addressing secondary objectives. Statistical analyses for the primary objective will exclude patients who terminate protocol treatment prematurely (i.e. less than 6 vaccinations) without an unacceptable toxicity.

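### The primary toxicity percentage counts a patient who stops before vaccine #6 only if that patient had the event, and no all-vaccinated estimate is planned beside it

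*Combined protocol and SAP*

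**What the plan says.** Section 15.4.2 states that a patient who discontinues before six vaccines "will not be evaluable for the primary endpoint, unless the patient experienced an unacceptable toxicity". Section 15.1 agrees: analyses for the primary objective "will exclude patients who terminate protocol treatment prematurely (i.e. less than 6 vaccinations) without an unacceptable toxicity". Section 15.1 gives the wider set, everyone who received any protocol treatment, to the secondary objectives only.

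Section 9.6 defines the same evaluable set more narrowly. It keeps an early stopper only if the unacceptable event was related to vaccine, or to vaccine plus TMZ. The endpoint definition in 9.1.1 and 15.4.1 also allows for RT, and places no vaccine attribution on Grade 4 toxicities.

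Under that definition a Grade 3 event attributed to treatment counts only if it is still unresolved at 3 weeks, apart from hypersensitivity needing steroids. Section 12.6.1 lists "Development of intolerable symptoms" and "Failure to tolerate TMZ therapy" as withdrawal reasons in their own right, beside unacceptable toxicity.

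On replacement, 15.4.2 says of the non-evaluable patients: "Per Section 12.6.3, these patients will be replaced". Section 12.6.3 itself covers only voluntary withdrawal before three vaccinations and investigator withdrawal before treatment. For the review of the first six patients, 15.4.2 adds: "If a patient who has not experienced an unacceptable toxicity does not complete 3 vaccinations, that patient will be replaced for initial study monitoring".

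**The concern.** Having the event is one of the two ways into the denominator, and staying to vaccine #6 is the other. A patient who leaves after four vaccines is counted if toxic and dropped if not. The resulting percentage describes neither everyone exposed to the vaccine nor a cohort fixed before outcomes were known, and it lies above the all-treated rate whenever anyone leaves early without the event.

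A second gap sits beside it. A patient may stop early because of, say, a Grade 3 event that resolves within 3 weeks. That patient is in neither the numerator nor the denominator, so a reader of the primary result cannot see that treatment was not tolerated.

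This is a first-in-human vaccine and the percentage is its headline safety result. No all-vaccinated or sensitivity estimate is specified for it. Nor is a confidence interval, although Section 15.6 asks for 95% intervals on exploratory proportions.

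**Working it through.** **Inputs from the plan (15.4.2).** Up to 28 treated; goal of 20 with at least six vaccines; expected drop-out before vaccine #6 below 20%; 18% used as the unacceptable-toxicity rate on TMZ in the suspension calculation.

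**The plan's enrolment figure.** Twenty evaluable patients at 20% drop-out need 20/(1 - 0.20) = 25. The stated 28 is a ceiling and corresponds to 8/28 = 28.6% not reaching vaccine #6. That is slack and not an arithmetic error, but it sets the range worth examining.

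**Effect of the rule.** Let N be treated patients, X those with the event, and L those who stop before vaccine #6 without it. The planned figure is X/(N - L) and the all-treated figure is X/N. With p = X/N and d = L/N,

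X/(N - L) = p/(1 - d).

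This follows from 15.1 and 15.4.2. Under 9.6, early stoppers whose event is judged unrelated would leave the numerator and denominator as well.

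| p (assumed) | d = 10% | d = 20% | d = 28.6% |
|---|---|---|---|
| 10% | 11.1% | 12.5% | 14.0% |
| 18% | 20.0% | 22.5% | 25.2% |
| 35% | 38.9% | 43.8% | 49.0% |

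At p = 18% the shifts are 2.0, 4.5 and 7.2 percentage points. The standard error at n = 20 is sqrt(0.18 × 0.82/20) = 0.086, so the shifts are 2.0/8.6 = 0.2, 4.5/8.6 = 0.5 and 7.2/8.6 = 0.8 of a standard error.

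**With counts (assumed), exact Clopper-Pearson 95% intervals, 28 treated and 8 event-free early stops.**
- Two events: planned 2/20 = 10.0% (1.2 to 31.7%); all vaccinated 2/28 = 7.1% (0.9 to 23.5%).
- Four events: planned 4/20 = 20.0% (5.7 to 43.7%); all vaccinated 4/28 = 14.3% (4.0 to 32.7%).

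**Which exits can occur when.** Section 9.1 gives vaccines #1 to #3 without TMZ, then surgery, then TMZ with or without RT. TMZ intolerance, the RT-period rules in Table 5 and failure to wean off steroids after surgery therefore all arise after vaccine #3. Of these tolerability exits, only one such as intolerable symptoms can remove a patient from the six-patient review. Between vaccines #3 and #6 the other routes are open. For patients with a higher grade at surgery, vaccine #5 falls during RT and #6 at its end, so chemoradiation precedes the cut-off.

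**Replacement.** A patient withdrawn by the investigator for TMZ intolerance after vaccine #3 is replaced according to 15.4.2, but falls outside 12.6.3, the section it cites.

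**The case against.** The strongest defence is that the rule errs on the safe side. For the endpoint as defined, dropping event-free leavers raises the percentage, and no test or decision threshold hangs on it. The data are not lost either. Table 3 counts patients accrued, not evaluable patients. All adverse events are collected from consent and summarised, with monthly investigator review. The reason for stopping treatment is documented, and the number of vaccines received is tabulated. This stands and lowers the severity. It does not correct the reported percentage, and Table 3 also counts only unacceptable toxicities.

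It is also fair that someone who leaves before TMZ was never at risk from the combination, so counting that person as a non-event dilutes the rate. That is a reason to show both estimates.

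A reader might go further in four ways that the documents do not support.

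- That the analysis set hides intolerance. It is the endpoint definition that does so: in an all-vaccinated set these patients would still be non-events. Counting them as events makes a different endpoint.
- That the six-patient review can pass by replacing patients who failed TMZ. TMZ and RT have not started by vaccine #3.
- That every such leaver is replaced, and every patient with the event is retained. Section 12.6.3 contradicts the first and Section 9.6 the second.
- That a sizeable share of patients leaves through intolerance. The drop-out figure covers all reasons and 28 is a ceiling; no split is given. Clinical decline or steroid dependence may reflect disease or surgery.

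**Conclusion.** The point holds in a limited form. Sections 15.1 and 15.4.2 make inclusion depend on the outcome and inflate the primary percentage, relative to all treated patients, by 1/(1-d): 1.11, 1.25 and 1.40 at d = 10%, 20% and 28.6%. The shift at 18% is below one standard error at n = 20.

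The size rests on two assumptions. One is d, which the plan does not give. The other is the 18%, which the plan takes from Grade 3 or 4 events on TMZ alone, a broader event than unacceptable toxicity. The direction, for the set in 15.1 and 15.4.2, needs neither assumption, only that there is at least one event and someone leaves early without one.

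That sub-threshold intolerance goes unreported in this percentage is a separate gap of unknown size. Section 9.6 disagrees with 15.1 and 15.4.2 on who is retained, and 15.4.2 disagrees with 12.6.3 on replacement. Severity is low to moderate.

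**What to change.** - In 15.1 and 15.4.2, report the unacceptable-toxicity percentage with an exact 95% confidence interval in all patients who received at least one vaccine, beside the six-vaccine evaluable estimate.
- Tabulate stops before vaccine #6 by reason, with a separate line for stops due to an adverse event at least possibly attributed to treatment.
- Show any such stop before vaccine #3 to those reviewing the first six patients, whether or not the patient is replaced.
- Use one definition of the evaluable set in 9.6, 15.1 and 15.4.2, including how RT-related and unrelated events are treated.
- Reconcile the replacement statement in 15.4.2 with 12.6.3.

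The cost is wording changes and one extra table from data already collected. The drawback is that the all-vaccinated estimate includes patients with short exposure and may dilute the rate for vaccine with TMZ or RT, so the two estimates should be read together.

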15.4.3 Handling of missing values, censoring, and discontinuations

If a patient does not receive any vaccine treatment, they will be excluded from all analyses.

15.5 Secondary Objective

An important secondary goal of this study is to assess the immunogenicity of the PEP_{IDH1M} vaccine alone and in combination with adjuvant TMZ using ELISpot. Levels of immune response will be examined after 3 vaccinations (i.e., pre-surgery) as well as after 3 additional post-surgery vaccinations. In previous research, the mean (\pm SD) number of SFC per 10⁶ lymphocytes for cells cultured with no peptide in previous qualified assays has been 4.5 \pm 3.6. The mean (\pm SD) response for cells cultured with an irrelevant peptide (i.e., actin) has been determined to be 4.2 \pm 6.3. Values for cells cultured with IDH1 peptide, after subtraction of counts from cells cultured with no peptide, will be determined. A response will be considered positive if this value is greater than 20 SFC per 10⁶ lymphocytes after determining the level of detection in the IDH ELISpot. With 20 patients, there is 80% power to detect a difference of 4.17 SFC per 10⁶ lymphocytes between response for cells cultured in IDH1 peptide and those cultured without any peptide. This power calculation conservatively assumes the response to IDH1 peptide and no peptide to be independent, and did not adjust for multiplicity.

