8 OBJECTIVES AND ENDPOINTS

	Objective	Endpoint	Analysis		
Primary	To assess the safety of the PEP _{IDH1M} vaccine alone and in combination with adjuvant TMZ and/or XRT/TMZ in adult patients with progressive, resectable WHO grade II gliomas that are confirmed Grade II or transition to a higher grade glioma at the time of surgery.	The percentage of patients who experience an unacceptable toxicity defined as any Grade 3 toxicity at least possibly attributed to the vaccine (or vaccine + TMZ and/or RT) that does not resolve to baseline within 3 weeks, any Grade 3 hypersensitivity reactions requiring steroids, any Grade 4 toxicity, including neurologic events not due to progressive disease, or any life threatening-event not attributable to concomitant medication, co-morbid event, or disease progression.	See Section 15.4		
Secondary	To assess the immunogenicity of the PEP _{IDH1M} vaccine with adjuvant TMZ using ELISpot.	Mean difference in the number of SFC per 10 ⁶ lymphocytes for cells cultured with and without IDH1 peptide	See Section 15.5		
Exploratory	To describe PFS and OS.	Proportion of patients alive without disease progression 6 months after initial vaccine treatment; median progression- free survival and median overall survival.	See Section 15.6		
Exploratory	To determine if ELISpot results after vaccination predict PFS or OS.	Number of SFC per 10 ⁶ lymphocytes above pre-vaccine baseline is a predictor of PFS or OS	See Section 15.6		
Exploratory	To estimate radiographic response rate prior to surgical resection and PFS after resection using RANO criteria.	Proportion of patients with radiographic response (complete + partial response) observed prior to surgical resection. Proportion of patients alive without disease progression 6 months after resection.	See Section 15.6		
Exploratory	To determine if tumors are IDH1 negative by immunohistochemical analysis and microarray analysis at the time of post-vaccine surgery.	Proportion of tumors that are IDH1 negative at the time of surgery	See Section 15.6		
Exploratory	To characterize immunologic cell infiltrate in tumors at the time of post-vaccine surgery.	Median number of immunologic cell infiltrates at the time of surgery	See Section 15.6		

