9 INVESTIGATIONAL PLAN

9.1 Study Design

Subjects with radiographic and/or clinical progressive and resectable Grade II glioma with expression of IDH1^{R132H} from the primary tumor (initial diagnosis) will be enrolled after signing informed consent. After consent has been signed, **all** subjects will undergo standard of care vaccination with 0.5 mL of Td (tetanus and diphtheria toxoids adsorbed) intramuscularly (I.M.) into the deltoid muscle to ensure adequate immunity to the tetanus antigen. The tetanus vaccine will be obtained through Duke ICS Pharmacy.

Eligible subjects will undergo a 1-2 hour leukapheresis for immune monitoring. Within 48 hours of leukapheresis, subjects will receive a vaccine site pre-conditioning as a single dose of Td toxoid (1 flocculation unit, Lf, in a total volume of 0.4 mLs saline). This will be administered one day prior to receiving PEP_{IDH1M} vaccine intradermally (i.d.) to the RIGHT groin area (as described below). The peptide vaccine is administered in the groin area approximately 10 cm below the inguinal ligament as vaccine # 1. Subsequent vaccines will be given on day 15 ±3 days (vaccine #2) and day 29 ±3 days (vaccine #3). These injections will occur without TMZ. Each injection of the peptide vaccine will be given half on the right groin and half on the left groin.

Seven to 12 days after the 3rd vaccine, subjects will undergo surgical resection of tumor, which is part of the SOC for these subjects. If possible, the provider will take a photo of the injection site at the pre-op appointment seven to twelve days after the 3rd vaccine to document the subject's reaction to the vaccine. Tumor samples from the surgical resection will be evaluated as outlined in the Exploratory Objectives.

Based on tissue obtained at surgical resection, subjects with stable histologic grade at recurrence will then be treated with vaccine and adjuvant TMZ at a targeted dose of 50-100mg/m²/d for 21 days every 28 days for up to 12 cycles (please see Section 18.5 in the Appendices for TMZ). During monthly cycles of TMZ, subjects will receive the vaccine on day 22 (+ 2 days) for a maximum of 15 total vaccines (which includes the first 3 bi-weekly vaccines). Patients that have transitioned to a higher Grade brain tumor will receive TMZ and radiation therapy per standard of care and monthly vaccines.

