All Adverse Events will be collected from time of consent until the end of the treatment phase of the study. The treatment phase of the study will end 1 month after the last vaccine (Section 12.3). Patients will be followed only for overall survival, progression-free survival, and subsequent therapies thereafter. For higher grade gliomas undergoing RT (please see Section 18.4 in the Appendices for SOC RT), vaccine #4 will be given during the SOC clinic visit prior to initiating RT, and vaccine # 5 will be given 4 weeks later (± 1 week) during RT. Vaccine #6 will be given at the end of RT during the SOC clinic visit to review MRI and begin post-RT TMZ, if MRI stable. Then, subjects in this treatment group will receive vaccines monthly on day 22 (+2 days) with post-RT cycles of TMZ to a maximum of 15 vaccines.

For immune monitoring and biomarker testing, subjects will have blood collected, as described in Section 12, during the following times: prior to vaccine therapy (at leukapheresis visit), prior to surgical resection (at the pre-op screening visit), prior to either RT/TMZ or first cycle of adjuvant TMZ (at SOC clinic visit) depending on tumor pathology, at vaccine # 6, and at End of Treatment (follow-up visit 1 month after vaccine #15; If a subject decides to stop participating in the study prior to vaccine #15, blood will be obtained at that time, if possible; If a subject progresses prior to vaccine #15, blood will be obtained at that time, if possible). For genomic proteomic analyses, blood and tumor samples will be obtained as described below in Section 9.4.

Subjects will be imaged with contrast-enhanced MRI according to the SOC every 10 weeks (+/- 4 weeks) while on TMZ and afterward, per the treating neuro-oncologist's recommendation. RANO criteria will be used for assessment of pseudoprogression and tumor progression (please see Section 12.7.3 for further detail). Subjects demonstrating definitive progression will be removed from study.

In addition, to demonstrate quantitative repeatable measures of 2HG in IDH1+ gliomas, subjects will be imaged using magnetic resonance spectroscopy (MRS) at baseline (prior to vaccine #1 following consent), and up to 4 times prior to surgery (please see Section 9.5 below for further information).

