We plan to isolate circulating nucleic acids from the plasma of patients affected by glioma and attempt to detect tumor-specific circulating DNA containing the c.395G>A (R132H) mutation. We will follow the protocol as described by Boisselier, et al., Neurology 2012⁸³ for plasma collection. Twenty mLs of blood will be the appropriate amount for our analyses (should yield ~10mL of plasma). At the same time, we will collect peripheral blood for immune monitoring. Ideally, we would like to have these blood samples collected:

- (1) Prior to initiating vaccine therapy at the leukapheresis visit,
- (2) Prior to surgical resection at the pre-op screening visit,
- (3) Prior to first cycle of TMZ at the SOC clinic visit (confirmed Grade IIs), or prior to RT/TMZ at SOC clinic visit (higher Grade Gliomas),
- (4) Vaccine #6
- (5) End of Treatment (follow-up visit 1 month after vaccine #15). If a subject decides to stop participating in the study prior to vaccine #15, blood will be obtained at that time (if possible). If a subject progresses prior to vaccine #15, blood will be obtained at that time (if possible).

b) Study of 2-Hydroxyglutarate levels in patients with gliomas with IDH1 R132H:

The second approach to be used will be a mass spectrometry-based approach for detection of 2hydroxyglutarate (2-HG), a metabolite specifically produced by tumors with the IDH1 c.395G>A (R132H) mutation. This metabolite can be sensitively detected by mass spectrometry and has been found to be elevated in the tissue of IDH1 R132H-containing gliomas as well as in the plasma of other solid tumors containing the same mutation (cholangiocarcinoma, subsets of breast carcinoma). A small portion of the previously mentioned isolated plasma will be used for a LC-MS/MS based approach for sensitive detection of circulating 2-HG levels.

Tumor tissue – we are planning to obtain a snap-frozen tumor tissue sample after the surgical resection for possible presence of IDH1 mutation and gene up-regulation.

Tumor Sampling Analyses:

At the time of surgical resection, excess tumor tissue will be obtained through the Duke Biorepository, and IHC analyses will be performed to assess immunologic infiltrate which will be identified by cell type and reactivity state.

Table 2. Screening and On-Study Tests and Procedures

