 ⁵ Immune monitoring and Biomarker testing will be drawn before initiation of vaccine therapy (at leukapheresis visit), prior to surgical resection, prior to RT/TMZ and vaccine #4 or cycles of TMZ (depending on tumor pathology), at vaccine #6, and at end of treatment (at the follow-up visit 1 month after vaccine #15, at the time come off study treatment, or at progression, whichever comes first). Blood for immune monitoring and Biomarker testing will be placed in 14 yellow containing ACD and 1 red vacutainer tube for a total of 90 mLs delivered to the BTIP lab for processing (3 red tops will be drawn with leukapheresis instead). Genomic proteomic analyses will include tumor sample at surgery and 20 mLs of blood (3 yellow ACD tubes) drawn at leukapheresis visit, at the pre-op screening visit prior to surgery, and depending on tumor pathology at the SOC clinic visit prior to starting either RT/TMZ (and receiving the 4th vaccine) or the 1st cycle of TMZ, at vaccine #6, and at end of treatment (at the follow-up visit 1 month after vaccine #15, at the time come off study treatment, or at progression, whichever comes first).

⁶ To demonstrate quantitative repeatable measures of metabolism change in IDH1+ gliomas via a standardized MRS protocol, patients will be scanned on the research MR scanner at up to 5 time points per subject: baseline (after consent and before PEPIDHIM vaccine #1), and up to 4 times prior to surgery. Up to 5 MRS scans can be scheduled between consent and surgery, but they are not required to be scheduled on the same day as PEP_{IDH1M} vaccines #1-3.

⁷ Tissue obtained will be used to reconfirm the Grade and assess immunologic cell infiltration, antigen expression, and biomarkers for immunologic response, specifically IDH1 T cell response.

⁸ Only for those whose pathology reveals transition from Grade II to Grade III at time of surgery.

⁹ Monthly cycles of TMZ will be initiated and adjusted at the discretion of the treating neuro-oncologist.

¹⁰ For higher grade gliomas undergoing RT, vaccine #4 will be given during SOC clinic visit prior to initiating RT, and vaccine # 5 will be given 4 weeks later (± 1 week) during RT. Vaccine #6 will be given at the end of RT during the SOC clinic visit to review MRI and begin post-RT TMZ, if MRI stable. Then, subjects in this treatment group will receive vaccines monthly on day 22 (+2 days) with post-RT cycles of TMZ to a maximum of 15 vaccines.

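### The secondary ELISpot analysis contains no pre-vaccine comparison, so in a single-arm trial it cannot by itself attribute an IDH1 response to the vaccine

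*Combined protocol and SAP*

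**What the plan says.** Table 1 (Section 8) defines the secondary endpoint as a mean difference in SFC per million "lymphocytes for cells cultured with and without IDH1 peptide". Section 15.5 gives the time points: "Levels of immune response will be examined after 3 vaccinations (i.e., pre-surgery) as well as after 3 additional post-surgery vaccinations". It subtracts the no-peptide count from the IDH1-peptide count and adds a responder rule: "A response will be considered positive if this value is greater than 20 SFC" per million lymphocytes, once the assay's level of detection is known. Its power sentence concerns the IDH1 versus no-peptide difference: 4.17 SFC detectable with 80% power in 20 patients.

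A pre-vaccine reference appears only in an exploratory row of Table 1, where the number of SFC per million "lymphocytes above pre-vaccine baseline is a predictor of PFS or OS".

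The pre-vaccine material exists. Section 9.1 states "Eligible subjects will undergo a 1-2 hour leukapheresis for immune monitoring", and the first sample in the Section 12 blood schedule is "Prior to initiating vaccine therapy at the leukapheresis visit". In Section 9.1 the last two immune-monitoring draws are "at vaccine # 6, and at End of Treatment".

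**The concern.** The objective is the immunogenicity of the vaccine, which is a claim about change caused by vaccination. Every enrolled patient is vaccinated, so the only available reference for that change is the patient's own state before vaccine #1. The no-peptide well is a different kind of control: it handles spontaneous spot formation in the same blood sample. A patient whose T cells already recognised the IDH1 peptide before vaccination would show the same positive difference as one who acquired that recognition. The 20 SFC rule cannot tell these two patients apart either.

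The sponsor uses the missing comparison elsewhere. Section 7.2.6 notes, for the earlier EGFRvIII vaccine, that specific responses were absent before vaccination.

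The second time point is also ambiguous. Section 15.5 promises an assessment after three further vaccinations, but the scheduled draw is at vaccine #6 and the next is at End of Treatment. No section says whether the blood is taken before or after that dose. If before, the sample reflects five vaccinations, not six.

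**Working it through.** **Inputs from Section 15.5:** no-peptide wells, mean 4.5, SD 3.6; irrelevant-peptide (actin) wells, mean 4.2, SD 6.3; n = 20; power 80%; wells assumed independent. Alpha, sidedness, the test and the SD for IDH1 wells are not stated.

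**1. Reproducing the plan's figure.** Take 6.3 as the SD for IDH1 wells.
- SD of the difference = √(3.6² + 6.3²) = 7.256.
- Detectable difference, one-sided 5%, approximated as (t₀.₉₅,₁₉ + z₀.₈₀) × SD/√n = (1.729 + 0.842) × 7.256/√20 = 4.171. This matches the stated 4.17.
- Exact noncentral-t power at 4.17 is 0.797. A two-sided 5% paired test would have power 0.684 there and a detectable difference of 4.79.

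The figure is therefore consistent with a one-sided 5% paired t-test within a single visit. No pre/post term enters it.

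**2. What the contrast does if the vaccine has no effect.** Let *b* be the mean IDH1-minus-no-peptide difference already present before vaccine #1. The documents give no value for *b*, so the range is assumed. The probability of a significant result comes from the noncentral t with 19 df and noncentrality *b*√20/7.256, one-sided 5%:

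| Assumed *b* (SFC per million) | P(significant), no vaccine effect |
|---|---|
| 0 | 0.050 |
| 1 | 0.147 |
| 2 | 0.324 |
| 3 | 0.555 |
| 4.17 | 0.797 |

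**3. The responder rule.** Under a normal approximation with SD 7.256, P(value > 20) = 1 − Φ((20 − *b*)/7.256). This is 0.003 at *b* = 0 and 0.015 at *b* = 4.17. In 20 patients that is 20 × 0.003 = 0.06 and 20 × 0.015 = 0.3 expected false responders. Numerically the rule is much less exposed than the mean contrast, but it still cannot identify a patient who was above 20 before vaccination.

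**4. Precision of a change from baseline.** Assume SD 7.256 at both visits and correlation ρ between them (not in the documents). SD of change = 7.256 × √(2(1 − ρ)), which is 10.26 at ρ = 0 and 7.26 at ρ = 0.5. Change detectable with 80% power, one-sided 5%:

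| Pairs | ρ = 0 | ρ = 0.5 |
|---|---|---|
| 20 | 5.92 | 4.19 |
| 16 (assumed loss of 4 pairs) | 6.69 | 4.73 |

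**The case against.** The strongest reply is that little is missing. The pre-vaccine sample is scheduled and the exploratory endpoint already requires SFC above baseline, so the trial will produce the numbers that would reveal pre-existing reactivity. On that view the gap is a cross-reference. It is true that no data are lost, but the time points, contrast, responder rule and power of the secondary analysis are all written out without a baseline. Leaving the comparison implicit also lets it be chosen after the data are seen.

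Second, the assumed range for *b* is anchored to nothing observed, and such evidence as there is points towards zero. Irrelevant peptide (4.2) shows no excess over no peptide (4.5), and the EGFRvIII account, for a different antigen, reports no prior responses. This stands: the probabilities show how sensitive the contrast is, not what to expect in this trial.

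Third, the 20 SFC rule is only slightly exposed on average. This also stands, as the working shows.

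Fourth, baseline and later cells may not be interchangeable. Footnote 5 to Table 2 says of the immune-monitoring tubes that "3 red tops will be drawn with leukapheresis instead", while later visits use ACD tubes. The documents are not uniform here: the same footnote and Section 9.4 have three yellow ACD tubes drawn at the leukapheresis visit, and Section 9.4 gives immune monitoring among that blood's uses. This is a reason to check comparability, not to omit the baseline.

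Finally, 16 pairs is only an assumption. Section 15.4.2 aims for 20 patients with at least six vaccines, and Section 15.1 admits all treated patients with data to the secondary analyses.

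**Conclusion.** The concern holds. As written, the analysis of the only secondary objective cannot separate a vaccine-induced IDH1 response from reactivity present before vaccine #1. The defect lies in the analysis wording, not in sampling, and it does not touch the safety endpoint.

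Its practical size is unknown. With no pre-existing reactivity the planned contrast keeps its 5% error rate; at an assumed 2 SFC that becomes 32%. These figures rest on the quoted SDs, independent wells, normality and a one-sided 5% test inferred from the 4.17. The change should be made, because it is cheap and the result cannot otherwise be attributed to the vaccine. The order of the vaccine #6 draw and dose is a separate, smaller ambiguity that one sentence would settle.

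**What to change.** Keep the within-visit contrast and its power statement. In Section 15.5 and the secondary row of Table 1:

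- Add the paired within-patient change in background-subtracted SFC, from the pre-vaccine leukapheresis-visit sample to the pre-surgery sample and to the vaccine #6 sample.
- Report the proportion of patients above 20 SFC before and after vaccination.
- State whether the vaccine #6 blood is drawn before or after that dose, and align Section 15.5 with the schedule.
- State which baseline cells are used, and confirm that they and the later tube-drawn cells behave alike in the assay. If this cannot be shown, label the change descriptive.
- Name the test, alpha, sidedness and assumed IDH1-well SD in the power sentence.

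The cost is SAP wording, a baseline ELISpot that the exploratory endpoint already needs, and the comparability check. No new sampling visit is required. The change score may be less precise than the within-visit contrast if the correlation between visits is low, and patients lacking either sample drop out of it. The existing powered contrast is unaffected.
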